5.7 Diet

Subjects should maintain a normal diet unless modifications are required to manage an AE such as diarrhea, nausea, or vomiting. Patients are to be instructed to refrain from using alcohol while enrolled in this study. Consumption of grapefruit and/or grapefruit juice should be avoided during the treatment period.

5.8 Reproductive Information

Participants of childbearing potential who are sexually active and their partners must agree to (1) abstain from heterosexual intercourse or (2) use 2 forms of effective methods of contraception as outlined below (one from each list).

Primary Forms	Secondary Forms
tubal sterilization (tubes tied)	male latex condom with or without spermicide
partner's vasectomy	diaphragm with spermicide
intrauterine device (IUD)	cervical cap with spermicide
hormonal contraceptives- (includes transdermal patch, injectables, implantables)	vaginal sponge (contains spermicide)

Female participants of child bearing potential must agree to use contraception from the time of informed consent, during the study and for 3 months after the last dose of study drug(s). Male participants must agree to use contraception from the time of initiation of study treatment, during the study and for 3 months after the last dose of study drug(s).

6 DOSE DELAYS/DOSE MODIFICATIONS

Toxicity and adverse events will be classified according to NCI's Common Terminology Criteria for Adverse Events Version 5.0 (CTCAE v.5). Subjects will be evaluated for adverse events (all grades), serious adverse events, and adverse events requiring protocol therapy interruption or discontinuation at each study visit for the duration of their participation in the study.

6.1 Start of a New Cycle

A new treatment cycle will only be initiated when all of the following conditions are met:

- ANC $\geq 1,500/\text{mm}^3$
- platelets $\geq 100,000/\text{mm}^3$
- non-hematologic treatment related toxicities have improved to \leq Grade 1 or to the patient's baseline values (except alopecia)

If blood counts are below this threshold, blood work is to be repeated weekly until counts are at an acceptable level. Treatment will be restarted with appropriate dose modifications. If treatment is unable to restart within 4 weeks of the planned treatment date, the patient will be permanently discontinued from study therapy. **NOTE:** For Cycle 1 of the Phase 1b study only, the inability to restart therapy within 2 weeks of the planned date is a DLT (per section 5.1.2); however the patient is allowed an additional week of recovery and is allowed to remain on study if treatment restarts within 4 weeks.

For subjects who present to the clinic with toxicity during a current treatment cycle, the study drug may be stopped per the discretion of the site investigator if the toxicity is determined to be clinically significant.

Dosing interruptions are permitted in the case of medical / surgical events or logistical reasons not related to study therapy (e.g., elective surgery, unrelated medical events, patient subject vacation, and/or holidays). Subjects should be placed back on study therapy within 4 weeks of the scheduled interruption, unless otherwise discussed with the sponsor-investigator. The reason for interruption should be documented in the patient's subject's study record.

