6.3 Dose Modifications for Entrectinib Toxicity

Dose Modifications for Entrectinib-Related Adverse Events

Toxicity*	Grade 1	Grade 2	Grade 3	Grade 4
Non-hematologic	Continue at same dose level	Continue at same dose level	Withhold dose until toxicity is \leq G1 or has returned to baseline, then reduce by 1 dose level and resume treatment	Withhold dose until toxicity is \leq G1 or has returned to baseline, then reduce by 1 dose level and resume treatment; or discontinue treatment as per the Investigator's discretion
Central Nervous System Effects	Continue at same dose level	Intolerable Grade 2; Withhold dose until recovery to \leq Grade 1 or to baseline. Resume at same dose or reduced dose, as clinically appropriate.	Withhold dose until recovery to \leq Grade 1 or to baseline. Resume at same dose or reduced dose, as clinically appropriate.	Discontinue treatment permanently

Hematologic	Continue at same dose level	Continue at same dose level	Withhold dose until toxicity is \leq G2, or has returned to baseline, then resume treatment at the same dose level or reduce by 1 dose level as per the Investigator's discretion Grade 3 lymphopenia without other dose-limiting events (e.g., opportunistic infection) may continue study treatment without interruption	Withhold dose until toxicity is \leq G2, or has returned to baseline, then reduce the dose by 1 dose level and resume treatment Grade 4 lymphopenia without other dose-limiting events (e.g., opportunistic infection) may continue study treatment without interruption
QT Interval Prolongation	QTc greater than 500 ms		Withhold entrectinib until QTc interval recovers to baseline. Resume at same dose if factors that cause QT prolongation are identified and corrected. Resume at reduced dose if other factors that cause QT prolongation are not identified.	
			Permanently discontinue entrectinib	
Vision Disorders	Grade 2 or above		Withhold entrectinib until improvement or stabilization. Resume at same dose or reduced dose, as clinically appropriate.	
Anemia or neutropenia	Grade 3 or 4		Withhold entrectinib until recovery to less than or equal to Grade 2. Resume at the same dose or reduced dose, as clinically appropriate.	

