6.4 Protocol Therapy Discontinuation

In addition to discontinuation from therapy related to toxicities as outlined above, a subject will also be discontinued from protocol therapy and followed per protocol under the following circumstances outlined below. The reason for discontinuation of protocol therapy will be documented on the electronic case report form (eCRF)

- If there is evidence of disease progression
- If the treating physician thinks a change of therapy would be in the best interest of the subject
- If the subject requests to discontinue protocol therapy
- If the protocol therapy exhibits unacceptable toxicity
- If a female subject becomes pregnant
- If there is a ≥ 4 week delay between cycles due to a treatment related adverse event.
- Subjects can stop study participation at any time. However, if they decide to stop, subjects will continue to be followed as per Section 7 calendar

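### At a cycle boundary, the entrectinib table (6.3) and the cycle-start criteria (6.1) give opposite instructions for the same persistent Grade 2 toxicity

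*Combined protocol and SAP*

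**What the plan says.** **Cycle start.** Section 6.1 opens with "A new treatment cycle will only be initiated when all of the following conditions are met". The conditions are ANC of at least 1,500/mm³, platelets of at least 100,000/mm³, and that "non-hematologic treatment related toxicities have improved to" Grade 1 or lower, or to the patient's "baseline values (except alopecia"). For low counts it adds: "If blood counts are below this threshold, blood work is to be repeated weekly until counts are at an acceptable level". It ends with a time limit: "If treatment is unable to restart within 4 weeks of the planned treatment date, the patient will be permanently discontinued from study therapy". The section speaks of study therapy as a whole and does not separate the two drugs. Sections 5.3 and 5.3.2 name 6.1 as the place where the cycle-start criteria are found.

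**Entrectinib toxicity table.** In Section 6.3, entrectinib goes on at an unchanged dose for Grade 2 events in the non-hematologic, hematologic and hepatotoxicity rows. For vision disorders of Grade 2 or above the instruction is: "Withhold entrectinib until improvement or stabilization. Resume at same dose or reduced dose, as clinically appropriate". For Grade 3 or 4 anemia or neutropenia it is: "Withhold entrectinib until recovery to less than or equal to Grade 2. Resume at the same dose or reduced dose, as clinically appropriate".

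**Schedule.** Sections 5.1 and 5.2 give entrectinib on Days 1 to 28 of a 28-day cycle (from Day 3 in Cycle 1 under 5.1 and 5.3.1), so no drug-free interval precedes the next Day 1.

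**Time limits.** Section 6.4 stops protocol therapy for a 4-week or longer "week delay between cycles due to a treatment related adverse event". Footnote b of the reduction tables in 6.2.1 (PAC-1) and 6.3.2 (entrectinib) stops treatment if the patient has not recovered after 2 weeks.

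**The concern.** A toxicity table and a cycle-start rule can coexist when the cycle has a rest period in which toxicity can settle. Entrectinib has none, so the two sections meet on every Day 1. Where 6.3 asks for neither a hold nor a dose change, 6.1 asks for a hold with a discontinuation deadline, although the subject's condition has not altered. Sites that follow different sections will give different exposure and record different numbers of toxicity discontinuations. Both matter for the safety objectives of a single-arm trial of 38 subjects. Because tumor imaging is scheduled by cycle number, a hold may also move or remove the first on-treatment scan.

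**Working it through.** The plan gives no figure on this point, so there is none to reproduce. The check sets the sections side by side and counts days.

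**1. The same event under each section**

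| Treatment-related event still present on Day 1 | Section 6.3 | Section 6.1 | Conflict? |
|---|---|---|---|
| Grade 2 non-hematologic, above baseline | Dose unchanged | No new cycle | Yes |
| Grade 2 hepatotoxicity, above baseline | Dose unchanged | No new cycle | Yes |
| Vision disorder stabilized at Grade 2 or above, above baseline | May resume | No new cycle | Yes |
| Neutrophils or platelets, Grade 2 | Continue, or resume after Grade 3 or 4 | No new cycle if below 1,500 or 100,000/mm³ | Only if Grade 2 includes such values |
| Anemia or lymphopenia alone | Row-specific | Not among the criteria | No |
| Non-hematologic toxicity at the patient's baseline, or alopecia | Row-specific | Cycle may start | No |

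The fourth row needs the CTCAE v5 cut-points, which the documents do not print. That part is therefore an assumption. The first three rows need no outside figure.

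**2. Day count** for a Grade 2 non-hematologic toxicity that begins in Cycle 1 and does not change:

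- Last dosing day of Cycle 1 under 6.3: Day 28.
- Planned Cycle 2 Day 1, where 6.1 applies: 28 + 1 = Day 29.
- 4-week limit in 6.1 and 6.4: 29 + 28 = Day 57.
- 2-week limit in 6.3.2, if a dose modification is needed: 29 + 14 = Day 43.

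The sequence is treat, hold, then discontinue if unresolved. The two time limits differ by 57 − 43 = 14 days.

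**3. Effect on imaging.** Footnote 6 of the Section 7 calendar places the first on-treatment scan before Cycle 3.

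- Cycle 3 Day 1 as planned: 2 × 28 + 1 = Day 57.
- If Cycle 2 starts up to 4 weeks late: 57 + 28 = Day 85. Three months is about 365/4 = 91 days (my conversion; the plan gives none).
- A subject discontinued during the hold never reaches Cycle 3. Imaging at the safety visit is at the site investigator's discretion (footnote 6), and later imaging is at physician discretion (footnote 13). With no post-baseline scan and no death, 9.9.3 censors at the last disease evaluation. Section 12.4.2 does not count the subject as evaluable for response unless progression was shown before the end of Cycle 1.

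**4. Size.** The documents give no rate of persistent Grade 2 toxicity, so the number affected cannot be derived.

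**The case against.** The strongest reply is that the plan does assign the decision. Section 5.3, which covers both drugs, refers to 6.1 for starting a cycle, and 5.3.2 repeats this for PAC-1. Section 6.1 is titled for that purpose, uses exclusive wording, deals with toxicity during a cycle in a separate paragraph, and says treatment restarts with suitable dose modifications. On this reading 6.3 manages toxicity within a cycle, 6.1 is a stricter check at each Day 1, and they apply in turn.

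Much of that stands. A reader might infer that no section governs the start of a cycle; 5.3 and 5.3.2 show otherwise. It does not remove the conflict. Section 6.3 is not limited to mid-cycle and does not refer to 6.1, and 5.3.1 on entrectinib does not repeat the reference given for PAC-1. The restart clause in 6.1 does not help either, because 6.3 prescribes no modification for these Grade 2 events. Even applied in turn, the sections give opposite instructions on consecutive days for an unchanged toxicity.

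Other stronger readings also fail:

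- *The subject is treated and taken off at the same moment.* Section 6.1 first holds treatment; discontinuation follows only after 4 weeks without a restart.
- *Full count recovery is required.* Only ANC and platelets are tested.
- *All Grade 2 toxicity continues under 6.3.* Grade 2 heart failure, pneumonitis, vision disorders and intolerable central nervous system effects are withheld.
- *Each affected subject moves the primary rate by 1/35 = 2.9 points.* The endpoint in 2.4.2 counts progression and death; a hold or a toxicity discontinuation is neither. Footnote 6 also has later tumor evaluations recorded where available. Discretionary imaging off treatment is a separate follow-up gap that this edit would not close.
- *Some 4 to 11 subjects are affected.* That needs an assumed 10% to 30% of 35 (35 × 0.10 = 3.5; 35 × 0.30 = 10.5). Nothing in the documents supports the range, and it would mix short holds with discontinuations.

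**Conclusion.** The inconsistency is real and should be corrected, but it is narrower than a general clash between the two sections. It arises when a toxicity is treatment-related, above the subject's baseline, still present on Day 1, and in a row where 6.3 continues or resumes entrectinib above Grade 1. For the non-hematologic, hepatotoxicity and vision rows this follows from the text alone. For neutrophils and platelets it holds only on the assumption that CTCAE Grade 2 extends below the 6.1 thresholds.

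The consequence is a hold of up to 4 weeks, then removal, for subjects whom the entrectinib table would keep on drug. How many is unknown. Exposure and toxicity discontinuation are affected directly. The timing or availability of the cycle-linked scan is affected possibly, and PFS events are not affected directly. The 14-day difference between the time limits adds a second ambiguity to the same decision.

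**What to change.** Reconcile 6.1 with 6.3. State, for each drug separately, whether the 6.1 recovery criteria override the continue and resume instructions in 6.3 at a cycle boundary, and which instructions apply within a cycle. Make the non-hematologic, hepatotoxicity, hematologic and vision rows consistent with that statement, and add a cross-reference between 6.3 and 6.1. In the same edit, reconcile the 2-week limit in 6.2.1 and 6.3.2 with the 4-week limit in 6.1 and 6.4, or say when each applies. Which recovery grade and which limit to adopt is for the sponsor's clinicians; this review takes no position.

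The cost is an amendment to the wording of Section 6 and a notice to sites. No new assessments, visits or subjects are needed.

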6.2 Dose Modifications for PAC-1 Toxicity

CTCAE v 5 Adverse Effects Terms & Descriptions)	PAC-1 Dose Modifications
Any other grade 3 non-hematologic toxicity	Hold dose until improvement to grade ≤ 1 then decrease dose by one dose level below level that caused toxicity.
Grade ≥ 2 neurologic toxicity detected at any time while on study treatment	Hold dose until improvement to grade ≤ 1 then decrease dose by one dose level below level that caused toxicity.
Any grade cerebrovascular ischemia or hemorrhage	Discontinue treatment.
Any other grade 4 non-hematologic toxicity	Discontinue treatment.
Neutrophils < 500 cells/mm 3	Hold dose until improvement to grade ≤ 1 then decrease dose by one dose level below level that caused toxicity.
Febrile Neutropenia	Hold dose until improvement to grade ≤ 1 then decrease dose by one dose level below level that caused toxicity.
Platelets $< 25,000/\text{mm}^3$ or platelets $< 50,000/\text{mm}^3$ with bleeding	Hold dose until improvement to grade ≤ 1 then decrease dose by one dose level below level that caused toxicity.
Any other grade 3 hematologic toxicity	Hold dose until improvement to grade ≤ 1 then decrease dose by one dose level below level that caused toxicity.
Any other grade 4 hematologic toxicity	Discontinue treatment.

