5.1.2 Definition of Dose-Limiting Toxicity

Toxicity and adverse events will be classified according to NCI's Common Terminology Criteria for Adverse Events Version 5.0 (CTCAE v.5).

Dose limiting toxicity (DLT) is defined as one of the following events **that are at least possibly related** to study medications occurring during Cycle 1 (first 28 days):

- Grade 3 or greater hematologic toxicity during the first cycle (28 days) of therapy.
- Cerebrovascular ischemia or cerebrovascular hemorrhage of any duration or grade.
- Grade 3 or greater clinical non-hematological toxicity (excluding \geq grade 3 nausea, vomiting, or diarrhea lasting less than < 72 hours with maximal medical intervention and/or prophylaxis) during the first cycle (28 days) of therapy.
- Delay of Cycle 2 treatment start by more than 2 weeks due to incomplete hematologic recovery ($ANC \geq 1.5 \times 10^9/L$ or platelets $\geq 100 \times 10^9/L$) or unresolved treatment related grade 3 or greater non-hematologic toxicity.
- Grade 2 or greater treatment related neurological toxicity occurring during the first cycle of therapy and lasting more than 72 hours.
- Hepatic labs meeting Hy's Law (concomitant elevations of AST/ALT and bilirubin of 3x ULN and 2xULN respectively without alternative etiology)

DLT's will be counted based on the number of patients with DLT at a given dose level, not the absolute number of DLTs. No single patient can trigger more than one DLT event. Additional patient cohorts will not be enrolled until all patients at the current dose level complete all planned treatment for Cycle 1 and are able to start Cycle 2 with no more than a 2-week delay.

Intra-subject dose escalation is not permitted. Once the MTD of PAC-1 in combination with entrectinib is determined, enrollment will continue until at least 6 subjects total are accrued at the maximum tolerated dose.

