6.2.1 PAC-1 Dose Reduction

Dose Reduction ^{a,b,c}	Dose	Dose
Starting Dose	750 mg daily	625 mg daily
First Dose Reduction	625 mg daily	500 mg daily
Second Dose Reduction	500 mg daily	375 mg daily
Third Dose Reduction	375 mg daily	250 mg daily
Fourth Dose Reduction	250 mg daily	NA

^a In the event a dose modification is needed, initiation of re-treatment should be delayed 1 to 2 weeks to allow for recovery from treatment-related toxicity

^b If the patient has not recovered after a 2-week delay, discontinue treatment

^c Up to four dose reductions are allowed if the starting dose is 750 mg. If subsequent cycles require additional dose reductions, treatment will be discontinued.

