4: A basic neurologic exam will be performed by the site investigator at screening, Day 1 of each Cycle of treatment and at the D30 safety follow up visit to monitor for neurologic toxicity. The Mini Mental Status Exam (MMSE) will be performed by a member of the research staff at screening and Day 1 of each Cycle of treatment to monitor for cognitive toxicity. The results of the MMSE and neurologic exam will be reviewed by the site investigator who will determine whether dose reduction of study drug(s) is required. This information should be retained.

5: CBC with differential and platelet to include: WBC, ANC, ALC, Hgb, PLT. Comprehensive metabolic profile (CMP) will be done at screening then Day 1 of each Cycle. During Cycle 1, a CMP should be performed at Cycle 1 Day 15. CMP to include glucose, calcium, BUN, creatinine, sodium, potassium, chloride, serum albumin, total bilirubin, alkaline phosphatase, AST, and ALT, ammonia, LDH and uric acid. Coagulation studies (PT/INR and PTT) will be done at screening then at the discretion of the treating investigator during treatment. For women of childbearing potential (WOCBP): urine or serum β hCG if clinically appropriate. If a urine test is done and it is positive or cannot be confirmed as negative, a serum pregnancy test will be required. Testing is required within 72 hours prior to initiation of study treatment. Urinalysis will be performed at screening.

6: Tumor response assessment will consist of evaluation by CT scans of chest and MRI or CT of abdomen and pelvis at screening and every odd numbered cycle starting after screening with CT scan before Cycle 3 (imaging selected for each subject should remain the same throughout the study); tumor imaging to be done at the safety follow up visit is at discretion of site investigator. If tumor assessments are available for subjects who have not yet experienced progressive disease (PD) at the time treatment is discontinued, the follow-up tumor evaluations will be documented in the eCRF until PD or death is confirmed, or until another treatment is initiated. MRI of the brain will be performed per standard of care for those subjects with a history of brain metastasis. A window of - 7 days may be used. CT/MRI images are to be submitted for central analysis. Images will be de-identified prior to sending to a central location. Central analysis to be performed upon receipt of funding.

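### The PAC-1 dose-modification table either allows re-treatment after a Grade 4 neurologic event (other than cerebrovascular ischemia or hemorrhage) or gives two conflicting instructions for it

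*Combined protocol and SAP*

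**What the plan says.** Three rows of the Section 6.2 table bear on the point:

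- Grade 2 or higher "neurologic toxicity detected at any time while on study treatment": hold PAC-1 until Grade 1 or less, then resume one dose level lower.
- Cerebrovascular ischemia or hemorrhage of any grade: discontinue.
- "Any other grade 4 non-hematologic toxicity": discontinue.

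The hematologic half of the table ends in the same way, with "Any other grade 4 hematologic toxicity" leading to discontinuation after several named hold-and-reduce rows. The table states no order of precedence among its rows.

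Other provisions limit re-treatment without settling the Grade 4 case. Section 6.2.1 footnote a sets a delay of 1 to 2 weeks before restarting, and footnote b adds: "If the patient has not recovered after a 2-week delay, discontinue treatment". Under Section 6.1, for clinically significant toxicity during a cycle, "the study drug may be stopped per the discretion of the site investigator". Section 6.4 lists as a ground for stopping: "If the protocol therapy exhibits unacceptable toxicity". Section 7, footnote 4, has the results of the neurologic and mental status exams reviewed by the site investigator, "who will determine whether dose reduction of study drug(s) is required".

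**The concern.** The neurologic row has a floor but no ceiling, so it takes in Grade 4. The row that would stop PAC-1 is worded as a residual category. Read together, they allow PAC-1 to be restarted after a life-threatening neurologic event, while a Grade 4 event in another non-hematologic system ends treatment.

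This runs against the rest of the plan, which treats neurologic toxicity more cautiously than other toxicity. Section 5.1.2 counts as dose-limiting "Grade 2 or greater treatment related neurological toxicity occurring during the first cycle of therapy and lasting more than 72 hours", whereas most other non-hematologic toxicity must reach Grade 3. Section 11.1.3.2 makes neurologic and cognitive disturbances of Grade 3 or higher the PAC-1 events of special interest.

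Patient safety is at stake. Section 10.1.6 describes brain vacuolation in dogs given PAC-1 that had not recovered 3 months after dosing ended. Clinical improvement to Grade 1 may therefore not show that the underlying injury has resolved. There is also a consistency problem: two sites could act differently on the same event and each could point to a row of the table.

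**Working it through.** No power or error-rate calculation applies. The check compares the rows with each other and with the neighboring sections, then reads the size of any re-exposure from the dose table.

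**Step 1. Action on PAC-1 by grade (Section 6.2).**

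| Event | Grade 2 | Grade 3 | Grade 4 |
|---|---|---|---|
| Neurologic, not cerebrovascular | hold, reduce | hold, reduce | hold, reduce |
| Other non-hematologic | no row | hold, reduce | discontinue |
| Cerebrovascular ischemia or hemorrhage | discontinue | discontinue | discontinue |

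Neurologic events are handled more strictly than other non-hematologic events at Grade 2, the same at Grade 3, and less strictly at Grade 4. The order reverses at the most serious survivable grade.

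**Step 2. Meaning of the residual wording.** In the hematologic half, neutrophils below 500, febrile neutropenia, and platelets below 25,000 (or below 50,000 with bleeding) each have a hold-and-reduce row. The closing Grade 4 row then covers what is left. The word *other* has work to do only if the named rows are outside it. The same reading in the non-hematologic half takes neurologic events out of the Grade 4 stop row.

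**Step 3. The alternative reading.** If the Grade 4 row is taken to include neurologic events, a Grade 4 neurologic event meets two rows. One says hold and reduce, the other says discontinue, and nothing ranks them.

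**Step 4. Search for a mandatory stop elsewhere.**

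- Section 6.2.1 footnote b stops only patients who have not recovered after a 2-week delay.
- Sections 6.1 and 6.4 rest on judgment or on toxicity called unacceptable, without a grade.
- Section 7 footnote 4 names only dose reduction as the decision that follows the exam.
- Section 5.1.2 governs Cycle 1 dose escalation, not re-treatment of an individual.
- Section 6.3 permanently stops entrectinib for Grade 4 central nervous system effects, but that table covers entrectinib only.

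None of these requires PAC-1 to stop for a Grade 4 neurologic event that recovers within 2 weeks.

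**Step 5. Comparison with entrectinib (Section 6.3).** General Grade 4 non-hematologic toxicity may be followed by a reduced dose of entrectinib, but Grade 4 central nervous system effects end it. For PAC-1 the order is the opposite. For a Grade 4 central nervous system event attributed to both drugs, entrectinib would stop for good and PAC-1 could resume.

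**Step 6. Size of the re-exposure (Section 6.2.1).** Resumed dose divided by the dose that caused the event:

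- From 750 mg: 625 / 750 = 0.833, or 83%.
- From 625 mg: 500 / 625 = 0.800, or 80%.
- If the dose had already been reduced: 375 / 500 = 0.750 (75%), or 250 / 375 = 0.667 (67%).
- Under the Grade 4 stop row: 0%.

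**The case against.** The strongest reply is that this is loose drafting and not a permission to re-treat. Read literally, Grade 2 or higher also includes Grade 5, which cannot improve to Grade 1, so the row was evidently not written as a full grade range. It can be read as a lower trigger for neurologic events, with the Grade 4 stop still applying on top. That reading is available, but it leads to the conflict in Step 3 and does not remove it.

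A second reply is that the rule may be deliberate, because the table accepts re-treatment after severe cytopenias and Section 6.3 accepts it after general Grade 4 non-hematologic toxicity. Against this, Section 6.2 is stricter for neurologic events at Grade 2, Section 6.3 stops entrectinib for Grade 4 central nervous system effects, and no rationale for a looser PAC-1 rule is given.

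A third reply points to oversight. Every Grade 4 event is a serious adverse event (Section 11.2.5), is reported within 1 business day (Section 11.3.2.1) and is promptly reviewed by the sponsor-investigator (Section 11.4). With at least a week before re-treatment, central notice should normally come before any restart. This does reduce the risk that sites diverge, but it gives notice and does not require a stop.

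Three limits stand:

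- The event should be uncommon. Section 10.1.6 reports no PAC-1-associated neurologic change in humans through 750 mg, and Section 1.4 gives 44 patients dosed.
- The one intracranial hemorrhage described in Section 10.1.7 would already fall under the mandatory cerebrovascular stop.
- The dog vacuolation was graded minimal to mild.

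The Section 6.3 precedent covers central nervous system effects only, so a stop for all Grade 4 neurologic toxicity is wider. That scope does match the breadth of Section 6.2's own Grade 4 non-hematologic row.

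**Conclusion.** The concern holds. For a Grade 4 neurologic event other than cerebrovascular ischemia or hemorrhage, Section 6.2 either permits PAC-1 to be resumed, at 83% or 80% of the causative dose from the two starting levels, or gives two incompatible instructions.

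The first outcome rests on reading the residual row as excluding events with their own row. The second follows if that reading is rejected. In both cases re-treatment also depends on recovery to Grade 1 or less, on no more than a 2-week delay, and on the investigator choosing to resume.

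No event rate can be given, and the dose percentages describe exposure, not risk. The point does not touch the sample size or the primary analysis. It is a safety clarification that should be made because it is cheap and concerns the organ system of greatest nonclinical concern for this drug.

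**What to change.** In Section 6.2, limit the neurologic hold-and-reduce row to Grade 2-3 and add a row stating that Grade 4 neurologic toxicity discontinues PAC-1. Leave the any-grade cerebrovascular row unchanged. This agrees with the Grade 4 non-hematologic row of the same table and, for central nervous system events, with Section 6.3. If the sponsor does intend re-treatment at Grade 4, the protocol should say so and give the reason.

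The cost is a one-row wording change by amendment. The downside is that a subject whose Grade 4 neurologic event resolves quickly loses the option of reduced-dose PAC-1, an option that Section 6.2 already denies after other Grade 4 non-hematologic toxicity.
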